7.2. Principal Secondary Efficacy Analyses

7.2.1. Endpoint / Variables

| Principal Secondary | |
|--|--|
| Objectives | Endpoints |
| 
 • To compare the proportion of participants achieving increases in Hgb when treated with daprodustat versus placebo. | 
 • % of participants having a Hgb increase of ≥ 1.0 g/dL from baseline to EP. |
| 
 • To compare daprodustat to placebo for health related quality-of-life. | 
 • Mean Change in SF-36 Vitality domain between baseline and Week 28. |

7.2.2. Summary Measure

| Principal Secondary | |
|--|---|
| Endpoints | Summary Measure |
| 
 % of participants having a Hgb increase of ≥ 1.0 g/dL from baseline to EP. | 
 Relative response rate (Dapro vs Placebo) of % of participants having a Hgb increase of ≥ 1.0 g/dL from baseline to EP. |
| 
 Mean Change in SF-36 Vitality domain between baseline and Week 28. | 
 Mean treatment difference (Dapro – Placebo) in the Change in SF-36 Vitality sub-score between baseline and Week 28. |

7.2.3. Population of Interest

The target population is defined by the study's inclusion and exclusion criteria.

The secondary efficacy analyses will be based on the Intent-To-Treat population, unless otherwise specified.

7.2.4. Strategy for Intercurrent (Post-Randomization) Events

For the first principal secondary endpoint of % of participants having a Hgb increase of ≥ 1.0 g/dL from baseline to EP, a treatment policy strategy will be used in the analysis to include all on and off treatment Hgb values of the ITT populations, including values taken after rescue and IP discontinuation.

The following are the intercurrent events for the first principle secondary efficacy analysis:

- Death prior to the end of the EP (i.e. before Week 28 visit)
- Randomized treatment discontinuation prior to the end of the EP
- Use of non-randomized ESA medications for any reason including rescue prior to the end of the EP
- Receipt of blood transfusions prior to the end of the EP

Except for the intercurrent event of deaths prior to the end of the EP, a treatment policy strategy will be used in which all scheduled Hgb data recorded during the EP (Weeks 24-28) will be included in the primary efficacy analysis, regardless of discontinuation of study medication due to any reasons, and regardless of receipt of non-randomized ESA medications for any reason including rescue, or blood transfusions. For deaths, a hypothetical strategy will be used as described in Section [7.2.5.2](#)

The following are causes of missing Hgb data affecting the first principle secondary efficacy endpoint that are not due to intercurrent events:

- Study withdrawal prior to the end of the EP
- Permanent switching from clinic visits to remote visits prior to start to EP
- Intermittent missing Hgb values at one or more visits with the EP

Missing data will be imputed as described in Section [7.2.5.2](#).

For the second principal secondary endpoint of mean change in SF-36 vitality sub-score between baseline and Week 28, a hypothetical strategy will be used assuming subjects had not had intercurrent events specified below. Data collected after IP discontinuation will not be included in the statistical analysis and will be treated as missing data. The missing SF-36 vitality sub-scores will be imputed as outlined in Section [7.2.5.2](#).

The following are the intercurrent events for the second principle secondary efficacy analysis:

- Death prior to the end of the EP (i.e. before Week 28 visit)
- Randomized treatment discontinuation prior to the end of the EP

7.2.5. Statistical Analyses / Methods

Details of the planned displays are provided in [Appendix 10](#): List of Data Displays, and will be based on GSK data standards and statistical principles.

Unless otherwise specified, endpoints / variables defined in Section [7.2.1](#) will be summarised using descriptive statistics, graphically presented (where appropriate) and listed.

In addition, descriptive statistics for each individual item within the SF-36 vitality subscore will be generated (See Section [7.3.2.1](#)). Of particular interest are the items assessing if participants have a lot of energy, feel tired, and feel worn out. These concepts have been found to be important and relevant in this population [[Martin, 2011](#)].

7.2.5.1. Interim Analysis

No interim analysis is planned to occur.

7.2.5.2. Statistical Methodology Specification

| Endpoint / Variables |
|--|
| 
 • % of participants having a Hgb increase of ≥ 1.0 g/dL from baseline to EP. • Mean Change in SF-36 Vitality domain between baseline and Week 28 |
| Model Specification |
| 
 • For the first principal secondary endpoint of % of participants having a Hgb increase of ≥ 1.0 g/dL from baseline to EP, the EP Hgb value will be defined as the mean of all available Hgb values (on and off-treatment) during the EP (Week 24 to Week 28 inclusive). A Cochran-Mantel-Haenszel (CMH) chi-squared test, adjusting for treatment, and region (see Section 5.3), will be used to make comparisons between the treatment groups. A treatment policy strategy will be used in the analysis to include all on and off treatment Hgb values of the ITT populations, including values taken after rescue and IP discontinuation. • For the second principal secondary endpoint of mean change in SF-36 vitality sub-score |

CONFIDENTIAL

205270

between baseline and Week 28, a hypothetical strategy will be used which includes only on-treatment values and exclude the measures taken after IP disc/rescue medication. The SF-36 vitality sub-scores will be imputed if missing. An ANCOVA model will be used including factors for baseline score, treatment, and region.

Model Results Presentation

- For the first principal secondary endpoint, the number and % of participants having a Hgb (on and off-treatment) increase of ≥ 1.0 g/dL from baseline to EP by treatment group, relative response rate (daprodustat vs. placebo) and two-sided 95% CI will be provided along with the one-sided CMH p-value for the treatment group comparison.
- For the second principal secondary endpoint, each individual item within the SF-36 vitality subscore will be summarized using mean, standard deviation, minimum, P25, median, P75 and maximum at baseline, Week 8, Week 12, and Week 28 visit by treatment group. (See Section 7.3.2.1)
- For the second principal secondary endpoint, all available SF-36 vitality sub-score change from baseline values (on-treatment only) will also be summarized using mean, standard deviation, minimum, P25, median, P75, and maximum at Week 8, Week 12, and Week 28 visit. (See Section 7.3.2.1)
- For the second principal secondary endpoint, the LS means estimated from treatment difference, will be presented along with one-sided p-value and 95% CI. The number of participants contributing to the analysis and the associated mean and standard deviation of the baseline and Week 28 SF-36 Vitality sub-score value will also be displayed with the results of the model.
- For the second principal secondary endpoint, all available SF-36 vitality sub-score values (on-treatment) will be displayed graphically for each scheduled study Week 8, Week 12, and Week 28 visit using a line plot.
- For the second principal secondary endpoint, all available SF-36 vitality sub-score change from baseline values (on-treatment) will be displayed graphically for each scheduled study Week 8, Week 12, and Week 28 visit using a line plot. The line plot of mean values \pm standard errors by time will include horizontal reference line to identify zero change, and the number of participants by treatment group contributing to each mean value.
- SF-36 data will be summarized and analysed using both norm-based and traditional scoring, see Section 10.6.5 for details. The traditional scoring will be considered as the primary results and norm-based as supportive results.

Multiple Imputation HGB Increase ≥ 1.0 g/dL

- For the first secondary endpoint, the imputed data from the primary endpoint will be used for deriving the % of participants having a HGB increase of ≥ 1.0 g/dL from baseline to EP.

Multiple Imputation SF-36 Analysis

- For the SF-36 principle secondary endpoint, multiple imputation analysis will be performed using on treatment SF-36 values and conducted under a set of assumptions about missing sf-36 values (see Section 10.6.3).
 - Missing scheduled SF-36 data in both arms through Week 28 will be considered MAR and imputed using PROC MI procedure with NIMPUTE = 200 and FCS to generate 200 datasets. The seed for reproducibility is set to 205270. The imputations will be done by randomized treatment, include region as categorical covariate.
 - Week 28 SF-36 values will be computed and compared across treatment groups using the principle secondary ANCOVA model described above. Rubin's rules [Rubin, 1987]

CONFIDENTIAL

205270

- will be used to combine results of the imputed datasets using SAS PROC MIANALYZE procedure. As a result, a single estimated treatment difference and its standard error will be produced, with which a 95% CI will be calculated.
- Subjects with scheduled off-treatment SF-36 data will be imputed assuming they were on treatment.
 - The low and high cutoffs at SF-36 values of 0 and 100 for traditional scoring and 22.89 and 70.42 for norm-based scoring will be applied to all imputed SF-36 values.
 - For the SF-36 principle secondary endpoint supportive analysis imputing subjects who have remote/over the phone SF-36 visits during Week 28 and those subjects who were treatment interrupted prior to their Week 28 visit will be performed using on treatment SF-36 values and conducted under a set of assumptions about missing sf-36 values (see Section 10.6.3). This is a similar imputation strategy as outlined above but will be based on on-treatment SF-36 values and consider those subjects who completed SF-36 remotely/over the phone or who were treatment interrupted prior to Week 28 as missing.

Supportive Analyses

- For the first principal secondary endpoint, a supportive analysis using while alive and on treatment strategy (on-drug analysis) will be performed using a Cochran-Mantel-Haenszel (CMH) chi-squared test, adjusting for treatment, and region (see Section 5.3), will be used to make comparisons between the treatment groups. No imputation will be performed for this analysis.
- For the second principal secondary endpoint, a treatment policy strategy (on and off treatment) analysis will be performed using an ANCOVA model including all participants with on and off treatment values, including factors for baseline score, treatment, and region. This will be done for both traditional and norm-based scoring. No imputation will be performed for this analysis.
- For the second principal secondary endpoint, a while alive and on treatment strategy (on treatment only) analysis will be performed using an ANCOVA model including all participants with on treatment values, excluding subjects who IP discontinue/rescue, including factors for baseline score, treatment, and region. This will be done for both traditional and norm-based scoring. No imputation will be performed for this analysis.
- For the second principal secondary endpoint, an analysis imputing subjects who have remote/over the phone SF-36 visits during Week 28 and those subjects who were treatment interrupted prior to their Week 28 visit will be performed using an ANCOVA model including factors for baseline score, treatment, and region. This analysis will be based on the hypothetical strategy outlined above. This will be done for both traditional and norm-based scoring. This analysis will only be performed if at least 10% of the ITT population is identified to have remote/over the phone SF-36 visits during Week 28 and those subjects who were treatment interrupted prior to their Week 28 visit have observed week 28 SF-36 data.

Subgroup Analyses

- For the first principal secondary endpoint, subgroup analysis will be performed using all available Hgb values (on and off-treatment). A Cochran-Mantel-Haenszel (CMH) chi-squared test, adjusting for treatment and subgroup, will be used to make comparisons between the treatment groups. A treatment policy strategy will be used in the analysis to include all on and off treatment Hgb values of the ITT populations, including values taken after rescue and IP discontinuation. The imputed data from the primary endpoint will be used for deriving the % of

CONFIDENTIAL

205270

participants having a HGB increase of ≥ 1.0 g/dL from baseline to EP.

- For the second principal secondary endpoint, subgroup analyses will be performed using an ANCOVA model, including factors for baseline score, treatment, region, subgroup and subgroup treatment interaction. A hypothetical strategy will be used as defined above. The SF-36 vitality sub-scores after IP discontinuation will be imputed based on the conservative assumption that there is no change in the sub-scores after the intercurrent event, so the last available on-treatment values (or baseline values if there is no on-treatment values) will be used in the imputation. This will be done for both traditional and norm-based scoring.

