7.3. Method of Treatment Assignment

- Subjects will be stratified by region (Section 12.8 Appendix 8). Region at study entry is considered a stratification factor that is potentially prognostic of study endpoints. Following stratification all participants will be centrally randomized in a 1:1 fashion to receive either oral daprodustat or oral placebo.
- Once a randomization number has been assigned by the IRT system, it must not be re-assigned
- Study treatment will be dispensed at the study visits summarized in the SoA (Section 2).
- Returned study treatment should not be re-dispensed to the participants.

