10.4.2. Secondary Analyses

10.4.2.1. Principal Secondary Efficacy Analyses

Conditional on the primary endpoint achieving superiority at the one-sided 2.5% level, statistical testing will progress to the principal secondary endpoints which will evaluate superiority using a one-sided 2.5% significance level.

For the first principal secondary endpoint of % of participants having a Hgb increase of ≥ 1.0 g/dL from baseline to EP, a Cochran-Mantel-Haenszel (CMH) chi-squared test, adjusting for treatment, baseline Hgb, and the prognostic randomization stratification factor, will be used to make comparisons between the treatment groups. An “effectiveness” estimand will be used in the analysis to include all on and off treatment Hgb values of the ITT populations, including values taken after rescue and IP discontinuation.

For the second principal secondary endpoint of mean change in SF-36 vitality sub-score between baseline and Week 28, an ANCOVA model will be used to compare the difference in this endpoint between arms, including factors for baseline score, treatment and the randomization stratification factor. An “efficacy” estimand will be used in the analysis in which we include only on-treatment values and exclude measures taken after IP disc/rescue medication. For this endpoint, an alternative approach may be conducted that includes the development of a prior distribution for the effects of placebo based on external data to be combined with the data from this trial in a Bayesian framework in order to make inference on the effects of daprodustat. If such an approach is undertaken it will be fully described in the RAP prior to the breaking of the study blind.

In addition, descriptive statistics for each individual item within the SF-36 vitality sub-score will be generated. Of particular interest are the items assessing if patients have a lot of energy, feel tired, and feel worn out. These concepts have been found to be important and relevant concepts in this population[Martin, 2011].

Additional secondary/exploratory endpoints are listed in Section 4.

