2. SUMMARY OF KEY PROTOCOL INFORMATION

2.1. Changes to the Protocol Defined Statistical Analysis Plan

Changes from the originally planned statistical analysis specified in the protocol are outlined in [Table 1](#).

Table 1 Changes to Protocol Defined Analysis Plan

| Protocol | Reporting & Analysis Plan | |
|---|---|---|
| Statistical Analysis Plan | Statistical Analysis Plan | Rationale for Changes |
| 
 Mean Change in individual items of the SF-36 Vitality Domain from baseline. Mean Change in SF-36 Physical Function domain from baseline. | 
 % of participants having an improvement in SF-36 Vitality Domain \geq 6 from baseline at Week 28. Mean Change in individual items of the SF-36 Vitality Domain from baseline. Mean Change in SF-36 Physical Function domain from baseline | 
 Additional endpoint to analyse the SF-36 scoring. |
| 
 | 
 Mean Change in SF-36 Vitality domain between baseline and Week 28, utilizing TREAT historical control data | 
 Principle secondary endpoint for SF-36 to be based on hypothetical strategy with imputation. Utilizing TREAT historical control data moved to secondary endpoint. |
| 
 Mean change from baseline by domain and overall symptom score on the Chronic Kidney Disease - Anemia Questionnaire | 
 Mean change from baseline by domain and single items on the Chronic Kidney Disease - Anemia | 
 Removed overall symptom and added single item |

CONFIDENTIAL

205270

| Protocol | Reporting & Analysis Plan | |
|---|--|---|
| Statistical Analysis Plan | Statistical Analysis Plan | Rationale for Changes |
| (CKD-AQ) symptom questionnaire | Questionnaire (CKD-AQ) symptom questionnaire | |
| 
 Summary of frequency and dose of IV iron use | 
 Summary of frequency and dose of IV iron use, rhEPO and transfusion use | 
 Adding additional variables of interest |
| 
 | 
 New displays related to COVID-19 pandemic have been added | 
 Assessing the impact of the COVID-19 pandemic |

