| 
 Only include randomized subjects who have both baseline and at least one Hgb assessment during the EP in the primary Hgb analysis | 
 All randomized subjects will be included in the primary Hgb analysis by imputing missing post-baseline Hgb data using pre-specified multiple imputation approach | 
 Addressing the feedback from FDA |

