5.4. Examination of Covariates, Other Strata and Subgroups

- The following is a non-exhaustive list of covariates that may be used in summaries of demographics, descriptive summaries and statistical analyses.
- Additional covariates of clinical interest may also be considered.
- If the percentage of participants is small within a particular subgroup, then the subgroup categories may be refined prior to unblinding the trial.
 - If the category cannot be refined further, then descriptive rather than statistical comparisons may be performed for the particular subgroup
- The primary and principal secondary endpoints will be evaluated for a set of prespecified subgroups. Subgroup analyses are aimed to assess for consistency with the overall result, and they may have low power if the subgroup is small. Statistical models (ANCOVA or CMH chi-squared test) will be adjusted for the covariates used in the original analysis, subgroup, treatment and treatment by subgroup interaction. Point estimates and two-sided 95% CIs will be estimated (presented on Forest Plots) and the subgroup by treatment interaction p-value calculated. Subgroup analyses will not be adjusted for multiplicity.

| Subgroups (Based on status before randomization) | Categories |
|--|--|
| Age | <65 years, ≥65 years - <75 years, ≥75 years |
| Gender | Female, Male |
| Race Group | Summary tables: American Indian or Alaskan Native, Asian, Black, Native Hawaiian or Other Pacific Islander, White, Mixed Race Analysis: American Indian or Alaskan Native, Asian, Black, White (exclude Native Hawaiian or Other Pacific Islander and Mixed Race) |
| Ethnicity | Hispanic, non-Hispanic |
| Region | Per Section 5.3 |
| Baseline BMI | <30kg/m ² , ≥30kg/m ² |

CONFIDENTIAL

205270

| Subgroups (Based on status before randomization) | Categories |
|--|---|
| Baseline Weight | <75kg, ≥75kg |
| Baseline Hgb | <8.5g/dL, 8.5-<9g/dL, 9-10g/dL, > 10g/dL <9g/dL, 9-<10g/dL, 10-11g/dL, >11g/dL |
| Serum Iron Levels at Baseline | TSATs≥15% and Ferritin≥50 ng/mL vs TSATs<15% or Ferritin<50 ng/mL |
| Iron Replete Participants | TSATs≥20% and Ferritin≥100 ng/mL vs TSATs<20% or Ferritin<100 ng/mL |
| hsCRP | Quartile Analysis |
| Diabetic | Yes, or No |
| History of Heart Failure | Yes, or No |
| eGFR | <15, ≥15 |
| ADPKD (Autosomal Dominant Polycystic Kidney Disease) | ADPKD, non-ADPKD Note: Only used for analyses of eGFR |

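### Hgb responder endpoint: the SAP's subgroup rule contradicts SAP 5.4 and cannot yield the required interaction p-value, and the protocol's baseline Hgb adjustment is dropped from the main test without a record

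*SAP*

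**What the plan says.** **Subgroup analysis of the responder endpoint.** SAP 5.4 sets a general rule for the primary and principal secondary endpoints, naming both ANCOVA and CMH. Models are to be "adjusted for the covariates used in the original analysis, subgroup, treatment and treatment by subgroup interaction", with subgroup estimates, 95% CIs and an interaction p-value. Protocol 10.4.4 says the same. The endpoint-specific rule in SAP 7.2.5.2 (Subgroup Analyses) reads differently: "A Cochran-Mantel-Haenszel (CMH) chi-squared test, adjusting for treatment and subgroup, will be used". Region and the interaction are both absent.

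**Main test.** Protocol 10.4.2.1 specifies a CMH test "adjusting for treatment, baseline Hgb, and the prognostic randomization stratification factor". SAP 7.2.5.2 (Model Specification) specifies "A Cochran-Mantel-Haenszel (CMH) chi-squared test, adjusting for treatment, and region". SAP 2.1 states "Changes from the originally planned statistical analysis specified in the protocol are outlined in" its Table 1, and no row there mentions the covariates of this test.

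**Context.** Region is the only randomization stratum (Protocol 7.3: "Subjects will be stratified by region"). The endpoint is second in the fixed testing sequence, so the SF-36 vitality test depends on it (SAP 5.5). Table 1 of the SAP says "All randomized subjects will be included in the primary Hgb analysis by imputing missing post-baseline Hgb data", and for the responder endpoint "the imputed data from the primary endpoint will be used for deriving the % of participants" who respond. The main analysis set is therefore all randomized participants, about 300 per arm.

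**The concern.** The programmer has two incompatible instructions for the responder subgroups. Following the endpoint-specific one gives a single treatment test pooled over subgroup levels, although SAP 5.4 says the purpose of these analyses is to judge consistency with the overall result. The interaction p-value is required, but neither document names a method for it on this endpoint, so the method could be chosen after the data are seen.

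For the main test, an alpha-controlled analysis is adjusted one way in the protocol and another way in the SAP, with no reason given. Baseline Hgb remains in the primary ANCOVA, so the SAP does not treat it as irrelevant to Hgb change. If it is prognostic for response, leaving it out gives up some power in the test that gates SF-36.

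**Working it through.** **1. The plan's own figures.** Inputs from Protocol 10.2.1: 270 evaluable per arm, 30% versus 50%, one-sided 2.5%.

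- SE under the null = √(2 × 0.40 × 0.60 / 270) = 0.0422. SE under the alternative = √((0.30 × 0.70 + 0.50 × 0.50) / 270) = 0.0413.
- Power = Φ((0.20 − 1.96 × 0.0422) / 0.0413) = Φ(2.84) = 99.8%, consistent with the stated figure of more than 90%.
- Smallest significant difference from 30%: 1.96 × √(2 × 0.34 × 0.66 / 270) = 0.080, which matches the stated 8%.

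**2. The subgroup rules side by side.**

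| Source | Region | Subgroup | Interaction |
|---|---|---|---|
| SAP 5.4 and Protocol 10.4.4, general rule | yes (original covariate) | yes | yes, with p-value |
| SAP 7.1.5.1, primary endpoint | yes | yes | yes |
| SAP 7.2.5.2, SF-36 vitality | yes | yes | yes |
| SAP 7.2.5.2, responder endpoint | no | yes | no |

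Only the responder endpoint departs from the general rule.

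**3. What a CMH stratified by subgroup reports.** Constructed example: two equal subgroups, 150 per arm in each.

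Case A, 50% versus 30% in both:
- Each stratum has 120 responders among 300; observed minus expected is 75 − 60 = 15, variance 150 × 150 × 120 × 180 / (300² × 299) = 18.06.
- z = 30 / √36.12 = 4.99; pooled relative rate 1.67.

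Case B, 70% versus 30% in one subgroup and 30% versus 30% in the other:
- Observed minus expected is 30 and 0; variances 18.81 and 15.80.
- z = 30 / √34.62 = 5.10; pooled relative rate (105 + 45) / (45 + 45) = 1.67.

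The CMH result is almost the same in the two cases. The interaction is not. In case B the subgroup relative rates are 2.33 (95% CI 1.79 to 3.04) and 1.00 (0.71 to 1.41). The ratio of the two is 2.33 (1.51 to 3.61), with log SE √(0.0184 + 0.0311) = 0.2225, z = 0.847 / 0.2225 = 3.81 and p = 0.00014.

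The scale has to be stated as well. Rates of 40% versus 20% and 80% versus 40% share a relative rate of 2.0 but have odds ratios of 2.67 and 6.0. SAP 7.2.2 makes the relative rate the summary measure.

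**4. Effect of dropping baseline Hgb from the main test.** Simulation with 300 per arm, 1:1 within region, CMH without continuity correction, response defined as Hgb change of at least 1.0, and change SD 1.5 (Protocol 10.2.1). Assumed, not in the documents: region shares 10/30/25/15/20%, baseline Hgb mean 9.4 and SD 0.55 (23% below 9 g/dL), and a linear baseline effect. The comparison is region only versus region × (below 9, 9 or above).

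At 30% versus 50%, power is 99.9% region-only and 99.9 to 100% with region × Hgb. One-sided type I error is 2.3 to 2.8% for both.

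At 30% versus 42% (closed form 86.7%), results depend on R², the share of variance in Hgb change explained by baseline. With these SDs the implied slope has size √R² × 1.5 / 0.55.

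| R² | Slope size | Region only | Region × Hgb | Gain |
|---|---|---|---|---|
| 0 | 0 | 86.1% | 85.9% | −0.2 |
| 13.4% | 1.00 | 86.9% | 88.0% | 1.1 |
| 20% | 1.22 | 86.4% | 88.6% | 2.2 |

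At R² = 25%, two separate runs gave gains of 2.7 and 2.9 points. Monte Carlo SE is about 0.4 point per tabulated power figure.

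A slope of −1 means that final Hgb is unrelated to starting Hgb. With SD 0.55 this is R² = (0.55 / 1.5)² = 13.4%; with SD 0.75 it would be (0.75 / 1.5)² = 25%.

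**The case against.** The case for leaving the plan alone has real content.

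- **The protocol's test could not be run as written.** A CMH needs categories, and Protocol 10.4.2.1 gives none for baseline Hgb. The SAP uses a region-only CMH for its other responder-type endpoints too, so the change may be deliberate harmonisation. This stands as an explanation, but it is a reason to record the change.
- **Region-only is a sound test.** This stands fully. A reader might infer that dropping baseline Hgb makes the confirmatory test invalid or raises its type I error. Region is the only randomization stratum, and the simulated error stays near 2.5%.
- **Power.** A reader might infer a large loss by supposing that baseline explains half or more of the variance in Hgb change. With the SDs above, R² of 50 or 60% needs a slope of size 1.9 or 2.1. If negative, as regression toward a common level implies, participants who start lower would have to finish higher. Dosing in both arms is titrated toward one common target range, and nothing in the documents suggests such slopes.
- **Subgroups are exploratory.** They are unadjusted for multiplicity and may be descriptive when small. This stands, and a reader should not infer any effect on the testing hierarchy. It does not remove the contradiction.
- **The mock shells are not in the documents.** The shell for Table 2.31, the only listed display of this subgroup analysis, might define more output. For the same reason, the absence of a forest plot among Efficacy Figures 2.1 to 2.25, although SAP 5.4 calls for one, is only a side note. A shell would not cure the conflict between the two method statements.
- **Choice of interaction method.** SAP 5.4 fixes no scale, so relative rate or odds ratio is partly preference. This stands.

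**Conclusion.** Two points hold, of different weight.

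The responder subgroup rule is wrong as written. It contradicts SAP 5.4 and Protocol 10.4.4 by omitting region and the interaction, and its test cannot produce the p-value those sections require. The numerical example shows what the test cannot see; it is not a forecast for this trial.

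The loss of baseline Hgb from the main test is an unrecorded change to an alpha-controlled analysis, and reversing it is a nearly free improvement. There is no validity problem, and the planned effect is unaffected (about 99.9% power either way). At 30% versus 42% the gain is about 1 point at R² of 13% and about 3 points at 25%. These gains rest on assumed region shares, baseline distribution and R², and treat imputed outcomes as fully observed.

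**What to change.** **Subgroups.** Rewrite the responder sentence in SAP 7.2.5.2 to follow SAP 5.4. Use a regression model with treatment, the covariates of the final main analysis, subgroup and subgroup-by-treatment, dropping duplicate terms when the subgroup is itself a covariate. A relative-rate model, such as modified Poisson with robust SE, matches SAP 7.2.2; a logistic model is acceptable if the odds-ratio scale is stated. Fit it in each imputed dataset and pool by Rubin's rules, with a pooled multi-df Wald test where a subgroup has more than two levels. Report subgroup estimates with 95% CIs and the interaction p-value. Keep the allowance in SAP 5.4 for descriptive reporting of small subgroups.

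**Main test.** Keep CMH. Before unblinding, preferably restore baseline Hgb by stratifying on region × a stated two-level cut, for example below 9 and 9 g/dL or above, a boundary already used in Protocol 10.4.4 and in both category sets of SAP 5.4. If region only is kept, add a row with the reason to Table 1 of SAP 2.1. Align the on-drug supportive CMH with the choice; it is not itself a protocol departure.

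**Cost.** Wording and programming only; no new data. The two-level cut gives 10 strata, the smallest averaging about 600 × 0.10 × 0.23 ≈ 14 participants under the assumed shares. The four-level set in SAP 5.4 that starts below 9 g/dL would give 20, about 5 of them with fewer than 5 participants, so two levels are preferable. The subgroup model runs in 200 imputed datasets per subgroup, as the primary subgroup analyses already do.
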